9.9 Development safety update reports

Where appropriate, the IMP manufacturer will submit Development Safety Update Reports (DSURs). These reports will be prepared by the sponsor (or delegate). In the absence of this, the CI will provide DSURs once a year throughout the clinical trial, or as necessary, to the Competent Authority (MHRA), where relevant the Research Ethics Committee and the sponsor.

The report will be submitted within 60 days of the Developmental International Birth Date (DIBD) of the trial each year until the trial is declared ended

10 STATISTICS AND DATA ANALYSIS

10.1 Sample size calculation

The primary analysis of this study will be a superiority test between the long and short prime-boost interval schedules within each group of COVID-19 vaccines.

The sample size calculation is based on the current available data from the ongoing ChAdOx1 nCoV-19 trial. The data suggests the standard deviation of anti-spike IgG measured by standardised ELISA is 0.4 at D28 post boost. Though using a different validated assay, a study on immunogenicity among health care workers at 21 days after receiving two doses of ChAdOx1 nCoV-19 or BNT162b2 also reported a standard deviation of anti-spike IgG between 0.3-0.5 (Eyre et al. 2021).

The sample calculation is based on the following assumptions:

1. The minimum clinical difference to detect is 1.75-fold difference in GMC between the long and short prime boost interval schedules, i.e. 0.243 on log scale (base 10).
2. The standard deviation of GMC on log scale (base 10) is 0.4.

Based on the above assumptions, the study will need to recruit 75 participants who are seronegative at baseline in each arm to achieve 90% of power at two-sided 1.67% significance level. Analysis will be performed separately for each group of COVID-19 vaccines. The significance level was adjusted for 3 comparisons using Bonferroni correction. We assume ~25% of study participants will be excluded from the primary analysis due to being seropositive at baseline or to loss of follow-up. Therefore, the sample size in

each arm will be expanded to 100 to give a total of 200 participants for each vaccine included. The total sample for 3 vaccines will be 600. Cohort 3 and cohort 4 will be used for exploratory analyses to generate hypotheses, and thus no formal sample size calculation was carried out. We aim to recruit up to 100 pregnant women in each of these 2 cohorts. This sample size was chosen based on practical constraints.

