10.3.2 Primary outcome analysis

The immunogenicity data is expected to be highly skewed with possible censored data at the lower detection threshold. A value half the lower detection threshold will be used to impute the data, and the data will be log-transformed prior to analysis. The geometric mean concentration and associated 95% confidence interval will be summarised for each arm, by computing the anti-log of the mean of the log-transformed data.

The primary endpoint is anti-spike IgG at delivery. The geometric mean concentrations (GMC) of anti-spike IgG will be compared between “short” and “long” prime-boost interval arms for each of the COVID-19 vaccine groups under the hypothesis:

H0: $GMC_{long} / GMC_{short} = 1$ or $\log_{10} GMC_{long} - \log_{10} GMC_{short} = 0$;

H1: $GMC_{long} / GMC_{short} \neq 1$ or $\log_{10} GMC_{long} - \log_{10} GMC_{short} \neq 0$.

For each vaccine groups (Pfizer / Moderna / Novavax / etc.), we will test the above hypothesis using a linear regression model adjusting for randomisation design variables. We will combine cohort 1 and cohort 2 in the primary analysis, and thus 3 regression models will be fitted. Sensitivity analysis will be carried out to further adjust for other covariates, which will be pre-specified in the statistical analysis plan. If a very high proportion (20%) of censored data are observed in the primary endpoint, then consideration will be made to use an alternative outcome as primary outcome, such as live neutralising antibodies against SARS-CoV-2.

The primary analysis will be conducted on the modified intent-to-treat basis, i.e. we will only include people who were seronegative at baseline and whose primary endpoint delivery is available. Because of the multiple comparisons in this trial, a p-value of two-sided 0.0167 will be considered as the threshold of statistical significance for the primary endpoint. Residual analysis will be used to check model fit. If model fit is not satisfactory specification of model covariates will be examined or an alternative model will be used.

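### The 90% power rests on an SD measured 28 days after the boost, the endpoint is at delivery, and the primary model carries gestational age only as a two-level cohort

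*Protocol*

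**What the plan says.** Protocol section 10.1 sets the target difference: "The minimum clinical difference to detect is 1.75-fold difference in GMC between the long and short prime boost interval schedules, i.e. 0.243 on log scale". It assumes that "The standard deviation of GMC on log scale (base 10) is 0.4", and concludes that "the study will need to recruit 75 participants who are seronegative at baseline in each arm" for 90% power at a two-sided 1.67% level. Allowing for about 25% exclusions, this becomes 100 per arm.

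The SD has two sources. The first is the ongoing ChAdOx1 nCoV-19 trial: "The data suggests the standard deviation of anti-spike IgG measured by standardised ELISA is 0.4 at D28 post boost". The second is a study of health care workers 21 days after two doses, on a different assay, which "also reported a standard deviation of anti-spike IgG between 0.3-0.5". Both are early, fixed times after dose 2.

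Section 10.3.2 states: "The primary endpoint is anti-spike IgG at delivery". For each vaccine, with cohorts 1 and 2 combined, "we will test the above hypothesis using a linear regression model adjusting for randomisation design variables". Section 7.3.1 names the stratification factors for these cohorts as study cohort and study site. Tables 1 and 2 in section 2 define cohort by gestation at recruitment: 13 0/7 to 23 6/7 weeks and 24 0/7 to 27 6/7 weeks. Section 10.3.2 keeps further covariates for a sensitivity analysis.

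**The concern.** Delivery is a fixed point in pregnancy but not a fixed time after vaccination. Women enter anywhere from 13+0 to 27+6 weeks and receive dose 2 either 4 to 6 or 8 to 12 weeks later, so the time for antibody to wane before the sample differs widely between them. If antibody is falling over that period, the differences in elapsed time add to the spread seen at day 28. The SD behind the power statement contains none of this, and section 10.1 does not discuss it.

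The main baseline determinant of the elapsed time is gestational age at dose 1. The primary model sees it only as a two-level band, one of which is 11 weeks wide. At stake are a power statement that is not supported for the endpoint actually analysed and some precision that is free to recover. No bias or type I error problem is involved.

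**Working it through.** **Reproducing the planned sample size.** Inputs from section 10.1: difference log10(1.75) = 0.243, SD 0.4, two-sided alpha 0.0167, power 90%.

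- Normal approximation: n = 2 × (0.4/0.243)² × (2.393 + 1.282)² ≈ 73.2, so 74 per arm.
- Two-sample t-test (noncentral t): 75 per arm, power 90.2%.
- Allowing for 25% exclusions: 75/0.75 = 100 per arm.

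The stated figures reproduce from their own inputs.

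**Weeks from dose 2 to delivery.** Windows from Tables 1 and 2; birth at 40 weeks is an assumption.

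| | Earliest dose 2 (weeks' gestation) | Latest dose 2 | Weeks to delivery |
|---|---|---|---|
| Cohort 1, short | 13 + 4 = 17 | 23+6 plus 6 = 29+6 | 10.1 to 23 |
| Cohort 1, long | 13 + 8 = 21 | 32 (limit) | 8 to 19 |
| Cohort 2, short | 24 + 4 = 28 | 27+6 plus 6 = 33+6 | 6.1 to 12 |
| Cohort 2, long | 24 + 8 = 32 | 36 (limit) | 4 to 8 |

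The overall range is 4 to 23 weeks.

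**How much of that spread the model removes.** Simulation of 400,000 women. Assumptions: entry uniform over 13 to 28 weeks; intervals uniform within the permitted windows and gestation limits; birth at mean 39.5 weeks, SD 1.5. The SD of the gap between dose 2 and delivery is:

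- 4.41 weeks, adjusting for arm only;
- 3.05 weeks after adding cohort, so cohort removes 1 − (3.05/4.41)² ≈ 52% of the variance;
- 1.68 weeks after adding continuous gestational age, 86% removed in all.

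With the two cohorts equal in size, cohort alone removes about 63%.

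**Effect on SD and power.** With a half-life of H weeks, log10 antibody falls by b = 0.301/H per week. Taking the day-28 SD of 0.4 as independent of the gap, residual SD = √(0.4² + (b × gap SD)²). Power is for 75 per arm and a difference of 0.243.

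| Assumed half-life | b per week | SD, planned model | Power | SD with continuous gestational age | Power |
|---|---|---|---|---|---|
| 30 days | 0.0702 | √(0.16 + 0.214²) = 0.454 | 80% | √(0.16 + 0.118²) = 0.417 | 87% |
| 45 days | 0.0468 | 0.425 | 86% | 0.408 | 89% |
| 60 days | 0.0351 | 0.414 | 88% | 0.404 | 89% |
| 90 days | 0.0234 | 0.406 | 89% | 0.402 | 90% |

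**Power across the protocol's own cited SD range** (75 per arm): 99% at 0.3, 90% at 0.4, 81% at 0.45, 71% at 0.5.

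**Shift in the difference.** In the same simulation the mean gap is about 14.0 weeks in the short arm and 9.5 weeks in the long arm. Waning over the extra 4.5 weeks moves the long-minus-short difference by 4.5 × b: +0.32, +0.21, +0.16 and +0.11 log10 for the four half-lives.

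**The case against.** Adjusting the primary model for the stratification factors is standard practice. Cohort is itself a gestational-age band and already removes about half of the variance in elapsed time. The protocol promises a sensitivity analysis with further covariates and has a secondary objective on gestational age at vaccination and the interval to delivery. The gain from a continuous term is about 7 percentage points at a 30-day half-life but under 1 at 90 days, and the protocol gives no half-life. Waning also acts on the means: the long arm is sampled sooner after dose 2, and at the shortest half-life the resulting shift (0.32) exceeds the whole target difference (0.243).

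Most of this stands, and it limits the point. It does not supply a justification for 0.4 at delivery. Nor is the covariate an open matter for the statistical analysis plan, because section 10.3.2 fixes the primary model and confines other covariates to sensitivity analysis.

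Two stronger readings are tempting, and the protocol supports neither.

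- A reader might infer that the primary model ignores gestational age. It does not: cohort carries it, coarsely.
- A reader might infer that true power is 71%, or that 116 per arm are needed, because the cited range reaches 0.5. That range comes from 21 days after two doses and is centred on 0.4, so it is no evidence of a larger SD at delivery. Waning spread alone gives only about 0.41 to 0.45 here; an SD of 0.5 would need some other cause.

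**Conclusion.** The point holds in a limited form. The 90% power is correct arithmetic for an SD of 0.4, but that SD belongs to a different time point and the protocol does not justify it at delivery. For a fixed 1.75-fold difference, the spread in elapsed time brings power under the planned model to about 80 to 89%. Continuous gestational age at dose 1 restores it to about 87 to 90%. These figures rest on assumed half-lives of 30 to 90 days common to all women, uniform entry and birth at about 39.5 weeks, none of which the protocol gives.

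The net effect of waning on power cannot be determined from the protocol, since the same decay that widens the SD also changes the expected difference between arms. The power claim should therefore be made conditional; it has not been shown to be false.

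**What to change.** 1. In section 10.3.2, add gestational age at dose 1 as a continuous covariate to the primary model for each vaccine, alongside cohort and site. It is known before randomisation, since eligibility and cohort depend on it. Do not adjust for the time from dose 2 to delivery: it arises after randomisation and is partly determined by the allocated interval.
2. In section 10.1, state that 90% power is conditional on an SD of 0.4 at delivery, and show power across the cited range on both sides: about 99% at 0.3, 90% at 0.4, 81% at 0.45 and 71% at 0.5.

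The cost is one covariate already collected and a reworded power statement that reads less favourably. The sample size does not change.

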10.2 Planned recruitment rate

It is hoped that recruitment will be completed within a 2 month period, although as with all studies recruiting in pregnancy, the recruitment rate can be unpredictable. The target recruitment number will be 800 to be recruited across 15 sites. It is expected that each site will recruit on average 24 participants per month.

10.3 Statistical analysis plan

A fully detailed statistical analysis plan will be prepared and will be signed off by the Chief Investigator prior to conducting any data analyses.

10.3.1 Summary of baseline data and flow of patients

At the end of the study, a flowchart will be used to summarise the number of women approached, consented, assigned to the different study arms, receiving vaccinations at the planned times, completing the study protocol and analysed for the primary outcome, as recommended by the CONSORT statement (<http://www.consort-statement.org/>). Baseline data will be summarised by study arms.

10.3.2 Primary outcome analysis

The immunogenicity data is expected to be highly skewed with possible censored data at the lower detection threshold. A value half the lower detection threshold will be used to impute the data, and the data will be log-transformed prior to analysis. The geometric mean concentration and associated 95% confidence interval will be summarised for each arm, by computing the anti-log of the mean of the log-transformed data.

The primary endpoint is anti-spike IgG at delivery. The geometric mean concentrations (GMC) of anti-spike IgG will be compared between “short” and “long” prime-boost interval arms for each of the COVID-19 vaccine groups under the hypothesis:

H0: $GMC_{long} / GMC_{short} = 1$ or $\log_{10} GMC_{long} - \log_{10} GMC_{short} = 0$;

H1: $GMC_{long} / GMC_{short} \neq 1$ or $\log_{10} GMC_{long} - \log_{10} GMC_{short} \neq 0$.

For each vaccine groups (Pfizer / Moderna / Novavax / etc.), we will test the above hypothesis using a linear regression model adjusting for randomisation design variables. We will combine cohort 1 and cohort 2 in the primary analysis, and thus 3 regression models will be fitted. Sensitivity analysis will be carried out to further adjust for other covariates, which will be pre-specified in the statistical analysis plan. If a very high proportion (20%) of censored data are observed in the primary endpoint, then consideration will be made to use an alternative outcome as primary outcome, such as live neutralising antibodies against SARS-CoV-2.

The primary analysis will be conducted on the modified intent-to-treat basis, i.e. we will only include people who were seronegative at baseline and whose primary endpoint delivery is available. Because of the multiple comparisons in this trial, a p-value of two-sided 0.0167 will be considered as the threshold of statistical significance for the primary endpoint. Residual analysis will be used to check model fit. If model fit is not satisfactory specification of model covariates will be examined or an alternative model will be used.

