4 TRIAL DESIGN

This is a Phase II, multi-centre, randomised, single-blind, platform study evaluating the safety, reactogenicity and immunogenicity of COVID-19 vaccines in pregnant women participants in the UK.

The design is “adaptive” in that new COVID-19 vaccines may be included as soon as they are approved, and new schedules may be assessed as they become relevant or considered for implementation (e.g., one dose schedules in which the single dose is given earlier than 28 weeks’ gestation, etc).

Potential participants will be recruited through academic and NIHR clinical trials sites.

After signing informed consent, participants may be screened and enrolled. During the screening period nose/throat samples may be taken to detect SARS-CoV-2 by PCR, if the participant has any COVID-19 symptoms or significant exposure history.

Approximately 800 pregnant participants are planned for the study, but this will be dictated by the number of vaccines being evaluated. An effort will be made to enrol groups that are most affected by COVID-19, including ethnic minorities.

As determined by their gestation at recruitment (and whether they had already received a single dose of COVID-19 vaccine pre-pregnancy), participants will then be randomised to receive 1 or 2 intramuscular (IM) injections of either vaccine A or B or C (etc.), at one of two dosing intervals (see tables 1- 4).

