8.2 Regulatory status of the drug

VACCINE A – Pfizer BioNTech (BNT162b2)

The BNT162b2 vaccine received a conditional marketing authorisation from the European Medicines Agency on the 21st of December 2020.

VACCINE B – COVID-19 Vaccine Moderna

Approved for use under a temporary authorisation of the supply of an unlicensed vaccine; regulation 174 of the Human Medicines Regulations 2012.

VACCINE C- Novavax, NVX-CoV2373

No marketing authority or emergency use approval currently

VACCINE D - AstraZeneca COVID-19 vaccine (ChAdOx1 nCoV-19) (*only for participants who have received one dose of this vaccine pre-pregnancy)

Approved for use under a temporary authorisation of the supply of an unlicensed vaccine; regulation 174 of the Human Medicines Regulations 2012.

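### The fixed primary threshold of 0.0167 suits exactly three vaccines, but the protocol leaves their number open and gives no rule for changing it

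*Protocol*

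**What the plan says.** Section 10.1 makes the primary analysis a long-versus-short superiority test within each vaccine. On multiplicity it says: "The significance level was adjusted for 3 comparisons using Bonferroni correction". It plans to "recruit 75 participants who are seronegative at baseline in each arm to achieve 90% of power at two-sided 1.67% significance level", and expands 75 to 100 per arm for about 25% exclusions, so 200 per vaccine and 600 for three.

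Section 10.3.2 carries the same level into the decision rule: "a p-value of two-sided 0.0167 will be considered as the threshold of statistical significance for the primary endpoint". It also says that "thus 3 regression models will be fitted".

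Other text leaves the number of vaccines open:

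- The sentence in 10.3.2 that introduces the test begins "For each vaccine groups (Pfizer / Moderna / Novavax / etc", which is an open list.
- Section 4 says "new COVID-19 vaccines may be included as soon as they are approved" and makes the trial's size depend on how many vaccines are evaluated. The trial summary lists other approved vaccines among the investigational products.
- Section 7.3.1 says the randomisation will be adjusted when vaccines are added.
- The number could also fall. Section 8.2 says of Novavax: "No marketing authority or emergency use approval currently".

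Sample size is set per vaccine and the allocation is allowed to change. No comparable rule is given for the significance threshold.

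**The concern.** A Bonferroni threshold depends on the number of tests. Section 10.3.2 fixes the number that belongs to three tests, next to an open list of vaccines. With more than three, the constant is too lenient for the 5% that it implies; with fewer, it is stricter than it needs to be. A threshold chosen after some vaccines have been analysed would be open to the charge that the data drove it.

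There is a second, smaller matter. Having opted for family-wise control, the plan uses single-step Bonferroni. Holm's step-down procedure has the same 5% bound and never rejects less.

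**Working it through.** **Inputs.** From 10.1: difference 0.243 on the log10 scale (1.75-fold), SD 0.4, 90% power, two-sided 1.67%, 75 evaluable per arm, 25% exclusions. From 10.3.2: threshold 0.0167. Assumed: a family level of 5%, which 3 × 0.0167 = 0.0501 implies but the protocol does not state; and independent tests, because each vaccine has its own long and short arms and its own model, with no shared control.

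**The plan's own figure.** By normal approximation,

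n = 2[SD(z₁₋α/2 + z₁₋β)/δ]² = 2[0.4 × (2.394 + 1.282)/0.243]² = 73.2, so 74 per arm.

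The exact two-sample t test (noncentral t) needs 75: power is 89.7% at 74 and 90.1% at 75. Then 75/0.75 = 100. The sample size reproduces.

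**Threshold held at 0.0167 with K vaccines.** Family-wise error for independent tests = 1 − (1 − 0.0167)^K; the sum bound is 0.0167K. The last two columns show power at 75 per arm (exact t) and n per arm for 90% power (normal approximation) when each test is instead run at 0.05/K.

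| K | Family-wise error at 0.0167 | Sum bound | 0.05/K | Power at 0.05/K | n per arm at 0.05/K |
|---|---|---|---|---|---|
| 2 | 3.3% | 3.3% | 0.0250 | 92.6% | 68 |
| 3 | 4.9% | 5.0% | 0.0167 | 90.1% | 74 |
| 4 | 6.5% | 6.7% | 0.0125 | 88.2% | 78 |
| 5 | 8.1% | 8.4% | 0.0100 | 86.5% | 81 |

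With two vaccines, keeping 0.0167 costs 92.6 − 90.1 = 2.5 points of power per vaccine.

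**Holm against Bonferroni, K = 3.** One million simulated sets of three independent t tests, 75 per arm, family level 5%, the planned effect wherever an effect is present:

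| Vaccines with a true effect | Power per such vaccine, Bonferroni | Holm | All true effects shown, Bonferroni | Holm | Holm family-wise error |
|---|---|---|---|---|---|
| 3 | 90.2% | 95.4% | 73.3% | 87.9% | none possible |
| 2 | 90.1% | 92.4% | 81.2% | 85.8% | 4.6% |
| 1 | 90.1% | 90.2% | 90.1% | 90.2% | 4.8% |
| 0 | – | – | – | – | 4.9% |

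The chance of at least one rejection is the same for both methods.

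**Changing K part-way.** Suppose three vaccines are tested at 0.0167, and a fourth is added later and tested at 0.05/4 = 0.0125. The family-wise error is 1 − (1 − 0.0167)³(1 − 0.0125) = 6.1%, with a sum bound of 3 × 0.0167 + 0.0125 = 6.26%. That is hardly better than the 6.5% from leaving the threshold alone.

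**The case against.** For the trial as specified, the family is three. Section 10.1 adjusts for three comparisons and totals 600 for three vaccines, 7.3.1 randomises among three, and 10.3.2 fits three models. Adding a vaccine would need changes to products, randomisation and sample size. Section 13.10 provides the amendment route, and the level could be reset there or in the SAP that 10.3 requires before any analysis. With no shared control, it is also a matter of judgement whether a later vaccine belongs to the same family.

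Most of this stands. A reader might infer that the protocol's stated error control fails. The text does not support that: it states an adjustment for three comparisons, and nowhere promises 5% across an open-ended platform. But the threshold was written into the protocol as a number, not deferred. It sits beside an open list of vaccines, and the protocol says neither which vaccines form the family nor what happens when their number changes.

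A reader might also infer that Bonferroni is a mistake here, or gives up power for nothing. Neither holds. It is valid for three vaccines, the trial was sized for it, and the 90% target is met. It also lets each vaccine be judged and reported on its own data, with simple matching confidence intervals. The largest Holm gain, 87.9% against 73.3% for showing all three effects, concerns a goal that the protocol does not set, because 10.1 analyses each vaccine separately. The two-vaccine case does little harm: the error rate falls to 3.3% and the power target is still met.

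**Conclusion.** The point holds in a limited form. The constant 0.0167 matches the chosen control only for exactly three vaccines, and the protocol leaves that number open. If all vaccines are one family at 5%, the departure is modest: 3.3% family-wise error with two, 6.5% with four, 8.1% with five.

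Holm is an inexpensive improvement to a valid plan. It adds about five points of power per vaccine at best, about two if two vaccines have the effect, and almost nothing if one does.

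These figures assume independent tests, the planned effect and SD for every vaccine that has an effect, and 75 evaluable per arm. The same error rate here means the same 5% bound: the actual error of the two methods is equal only when no vaccine has an effect.

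**What to change.** In 10.3.2, replace the constant with a rule: *Holm procedure at two-sided family-wise 5% across the K vaccines randomised concurrently and analysed together, with K and the members of the family fixed before any primary comparison is unblinded or tested.* This must be settled before the immunogenicity interim analysis in 10.4, which uses the primary endpoint.

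Add two provisions:

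- A vaccine that must be reported before the others is tested at 0.05/K, and Holm is not applied across separately reported vaccines. The rest share what remains, 0.05 − 0.05/K.
- A vaccine added after the family is fixed forms a separate, prespecified family, with its own level set in the amendment that adds it. K is not re-based, for the reason shown by the 6.1% above. State that the 5% guarantee then applies within each family.

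Keep the 0.0167 calculation in 10.1, described as conservative for up to three vaccines only. If K exceeds three, restate it: with four at 0.05/4, Bonferroni power at 75 per arm is 88.2%.

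The cost is a few sentences and no extra participants for up to three vaccines. The downsides are that Holm-adjusted intervals are less simple to present, and that Holm needs the p-values of the whole family together.
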